As shown in Figure 3, proposed is a 2X2 factorial randomized clinical effectiveness trial testing the effects of combining CM as an adjunct to state-of-the-art, evidence-based CBT (CBT + CM vs. CBT only) and the effects of a single, long-term incentive for bioverified abstinence/no heavy drinking at 6-months follow-up (Long Term Incentive vs. No Incentive). All patients will be referred to standard aftercare and encouraged to participate in 12-step programs following the intervention. Use of aftercare and other health care utilization will be collected based on objective measures (VA electronic medical record) and participant report. Health-related quality of life will be collected at each follow-up. The primary endpoint (AIM 1) will be number of heavy drinking days in the past 30 days at the 6-month follow-up. Cost effectiveness analysis (AIM 2) will be performed using quality-adjusted life years (QALY) as the outcome. The utility of a long-term incentive (AIM 3) will be tested by examining use of aftercare and other alcohol-related treatment and heavy drinking days in the past 30 days at the 6 and 12-month follow-ups.

D.2. Patient Identification, Eligibility, and Recruitment

Patients will be identified from the Durham VA Health Care System (DVAHCS) using the hospital's computerized medical record. Records will be screened for AUD. After mailing introductory materials with an opt-out number, we will contact those who do not opt out via telephone to explain the study and recruit them for participation. If necessary, in order to reach female veterans, we can oversample women for the screening mailouts.

Figure 3. Trial Design

We will also utilize reactive recruitment methods as needed to reach potentially eligible veterans. For example, we will seek referrals from the DVAHCS Substance Use Disorders Clinic. In order to reach female veterans, we will seek referrals from the Women's Health Clinic. In addition, we will post IRB-approved flyers and brochures throughout the DVAHCS catchment area, especially in clinic areas and Vet Centers. In addition, we will post, if necessary, flyers and brochures in the community, in local restaurants, laundromats, university student centers, etc. We will also use online classified advertisements such as Craigslist.com to reach potential participants.

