Aim 1: To examine the first hypothesis that CM will be associated with greater treatment engagement and treatment completion than the control condition, treatment engagement will be defined as the number of counseling sessions completed, with treatment completion defined as completion of all 12 counseling sessions. Potential group differences in treatment engagement as a function of counseling sessions completed will be examined using independent *t*-tests. Contingency-table analysis will be used to examine whether a greater proportion of the CM participants complete the treatment in comparison to the control group. The second hypothesis is that CM will be associated with higher rates of self-reported abstinence and fewer heavy drinking days at 6 and 12 months. MLM will be used to model each of these outcomes. Specifically, logistic MLM will be

conducted to model abstinence as a function of treatment, time (categorized as end of treatment, 6 months, 12 months), and the interaction between treatment and time. Randomization to long-term abstinence incentive will be covaried. Linear contrasts will be specified at each time point to examine the hypothesis that CM will result in higher abstinence rates than CBT alone at 6 and 12 months. A similar count-based model (e.g., Poisson, negative binomial) will be conducted to analyze number of days of heavy drinking (per 30 days). In addition to modeling the effects of treatment, time, and the interaction between treatment and time, number of days of heavy drinking recorded at baseline and randomization to the long-term abstinence incentive will be covaried. Again, linear contrasts will be derived at each time point to compare treatment effects at 6 and 12 months.

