Power calculations provided below were performed with Power Analysis and Sample Size software (PASS, Version 12: NCSS LLC, Kaysville, Utah). The sample size estimate is based on the first hypothesis that the CM intervention will result in higher overall self-reported abstinence rates and fewer days of heavy drinking at 6-months post-randomization. As described in the analysis section, this hypothesis will be tested via linear contrasts specified within the context of MLM analyses. Because this will be tested using repeated-measures data, statistical power will depend on the effective sample size (ESS). The ESS is the number of statistically independent observations available for this study, which is equivalent to the total number of observations (number of participants x number of data collections) adjusted for within-individual correlations. As the intraindividual, or intra-class, correlation (ICC) decreases, the ESS increases. Given that we found an ICC of .20 for 7-day point prevalence measured at posttreatment, 3 months, and 6 months in an RCT with 218 smokers featuring CM as the experimental treatment (R01 CA196304), we anticipate a similar, if not smaller, figure in this trial, given longer intervals between observations. Using this ICC value, with 140 participants with up to 3 observations each, the ESS would be 300. Even with an unexpectedly high 15% attrition at each observation point, such that only 119 complete treatment, 101 6-month follow-up, and 86 12-month follow-up, the ESS for examining linear contrasts would be 227, which would be sufficient to detect treatment effects as small as Cohen's $d = 0.43$ with 90% power. Because the previous trial examining the effect of CM as an adjunct to behavioral treatment found large effects (Cohen's $d = 0.92$; McDonell et al., 2017) on heavy drinking days, our proposed sample size has sufficient statistical power.

G. PROJECT MANAGEMENT PLAN and TIMELINE

The scheduled project timeline is illustrated in Table 5. Members of this multi-disciplinary research team have experience in one or more key components of the

Activity	Year 1				Year 2				Year 3				Year 4				Year 5			
	1	2	3	4	1	2	3	4	1	2	3	4	1	2	3	4	1	2	3	4
Hire/Train Staff	■																			
Recruitment		■	■	■	■	■	■	■	■	■	■	■								
Intervention			■	■	■	■	■	■	■	■	■	■								
Follow-ups: post-txt, 6-and 12-months			■	■	■	■	■	■	■	■	■	■		■	■	■	■			
Data Analysis														■	■	■	■	■	■	■

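### The stated 90% power at d = 0.43 belongs to an effect pooled over three visits; the primary 6-month contrast has about 57% power at that effect under the plan's own attrition.

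*Combined protocol and SAP*

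**What the plan says.** Section D.1 fixes the endpoint at one visit: "The primary endpoint (AIM 1) will be number of heavy drinking days in the past 30 days at the 6-month follow-up". The power paragraph of Section F bases the sample size on the same time point, namely "higher overall self-reported abstinence rates and fewer days of heavy drinking at 6-months post-randomization", and says the hypothesis is tested by linear contrasts within the multilevel model.

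Section F, Aim 1 gives that model: treatment, time as a three-level category (end of treatment, 6 months, 12 months) and their interaction. The count model also adjusts for baseline heavy drinking days and for the long-term incentive. From it, "linear contrasts will be derived at each time point to compare treatment effects at 6 and 12 months".

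The power calculation then uses an ESS. The ICC comes from an earlier smoking trial, where "we found an ICC of .20 for 7-day point prevalence measured at posttreatment, 3 months, and 6 months". Before attrition, "with 140 participants with up to 3 observations each, the ESS would be 300". The attrition scenario is "15% attrition at each observation point, such that only 119 complete treatment, 101 6-month follow-up, and 86 12-month follow-up". After that attrition, "the ESS for examining linear contrasts would be 227, which would be sufficient to detect treatment effects as small as" a standardised difference of 0.43, the power being put at 90%. The paragraph concludes that 140 is enough because an earlier CM trial found d = 0.92.

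**The concern.** Repeated measures raise the information about a treatment effect only if the visits are pooled, that is, if one effect is assumed common to all visits or the visits are averaged. Once the model has a treatment-by-time term and the test concerns the arm difference at 6 months, the other visits help only indirectly, by predicting 6-month values that are missing. The plan gives the pooled information to a test that does not pool.

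Two things are at stake. First, a reader of a non-significant primary result would take from this paragraph that d of about 0.43 had been tested with 90% power. Second, Section F, Aim 2 runs the cost-effectiveness analysis only if the primary outcome is significant and otherwise switches to cost minimization. At a true d of 0.43 that switch would occur about 43% of the time (1 − 0.57), not the 10% implied by the stated power.

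**Working it through.** **Inputs.** From the power paragraph of Section F: 140 randomised, up to three observations each, ICC 0.20, and 119, 101 and 86 seen at the three visits (140 × 0.85 = 119; × 0.85 = 101; × 0.85 = 86). Two inputs are assumptions: two-sided alpha of 0.05 and 1:1 allocation for the CM factor. The documents state no alpha. Two-sided 0.05 returns the stated 90%; one-sided 0.05 would give 94% and does not.

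**Step 1: reproduce the plan's figure.** For a group of n people with m observations each, ESS = n·m / (1 + (m − 1)·ICC).

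- No attrition: 140 × 3 / 1.4 = 300.
- With attrition, 86 people have three visits, 101 − 86 = 15 have two, and 119 − 101 = 18 have one: 86 × 3/1.4 + 15 × 2/1.2 + 18 = 184.3 + 25 + 18 = 227.3.
- A two-sample t-test with N = 227 has power 0.897 at d = 0.43 (0.900 by the normal approximation). The effect detectable with 90% power is d = 0.432.

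So 300, 227 and 0.43 all reproduce. The arithmetic is sound.

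**Step 2: which effect does 227 describe?** Use generalised least squares with compound symmetry (correlation 0.20) and the same dropout pattern; per arm, 43 people have three visits, 7.5 have two and 9 have one. The per-arm information matrix for the three visit means is I = Σ n·Z′V⁻¹Z over the dropout patterns. Effective N is 4/SE², with SE the standard error of the arm difference in SD units.

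| Effect estimated | Effective N | Power at d = 0.43 (normal) |
|---|---|---|
| One effect, constant over the three visits | 227.3 | 90% |
| Average of the three visit-specific effects | 223.5 | 90% |
| 6-month effect, treatment-by-time in the model | 101.6 (SE 0.198) | 58% |

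The plan's 227 is exactly the first row. The primary test is the third.

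**Step 3: power of a single-visit contrast** (two-sample t, two-sided 0.05).

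| Participants at the visit | Power at d = 0.43 | Detectable d, 90% | Detectable d, 80% |
|---|---|---|---|
| 140 (no attrition) | 71% | 0.55 | 0.48 |
| 101 (6 months, plan's attrition) | 57% | 0.65 | 0.56 |
| 86 (12 months, plan's attrition) | 50% | 0.71 | 0.61 |

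**Step 4: sensitivity.**

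- *ICC.* With the plan's dropout, the 6-month contrast has effective N 105.0 at ICC 0.5 (power 60%) and 109.1 at ICC 0.7 (61%). A lower ICC, which the plan counts on to raise the ESS, moves this contrast towards N = 101.
- *Baseline adjustment.* Adjusting for a baseline value correlated r with the outcome turns d into d/√(1 − r²). The documents give no r. With 101 seen, power is 61% at r = 0.3, 70% at r = 0.5 and 85% at r = 0.7. Reaching 90% needs 0.43/√(1 − r²) = 0.651, so r = √(1 − (0.43/0.651)²) = 0.75. With all 140 seen, the same reasoning gives r = √(1 − (0.43/0.552)²) = 0.63.
- *Cited effect.* At d = 0.92 with 101 participants, power is 99.6%.

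**The case against.** The strongest reply is that the case for 140 participants does not depend on 0.43. The plan argues that the detectable effect lies well below the 0.92 seen earlier, and 0.65 is also below 0.92. That stands: if the true effect is near 0.92, the trial is well powered. It does not rescue the separate statement that effects as small as 0.43 are detectable with 90% power.

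The figure of 101 is also a pessimistic scenario. The plan calls this attrition unexpectedly high, and Section D.10 cites retention above 80% at 12 months in the team's own trials. With 112 seen (80% of 140), power at d = 0.43 is 62%; with 119 it is 64%. Complete follow-up gives only 71%, which is also the ceiling if missing outcomes are counted as heavy drinking, as Section D.10 says.

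Baseline heavy drinking is already a covariate in the count model, so the unadjusted 57% is the lower end of a range. This is fair, and the range is shown above. However, the plan's calculation takes no credit for this adjustment, gives no correlation to support any, and the abstinence model has no baseline drinking covariate at all.

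Finally, Cohen's d is only a rough scale for a Poisson or negative binomial model, whose power depends on a mean and dispersion the documents do not give. This applies equally to the plan's own figure. It limits the precision of every number here but does not close the gap between pooled and single-visit information.

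**Conclusion.** The concern holds. The ESS of 227 is correctly computed but answers a different question from the primary test. For the 6-month contrast under the plan's attrition, power at d = 0.43 is about 57%, not 90%, and the effect detectable with 90% power is d = 0.65. Without any dropout the figures are 71% and 0.55. They rest on two-sided alpha of 0.05 and 1:1 allocation (both assumed), a standardised continuous scale as the plan uses, and no credit for baseline adjustment. A baseline correlation of about 0.75 would be needed to reach 90% with 101 participants. The sample size remains adequate for an effect near 0.92. The sensitivity claim for smaller effects has to be corrected, because it governs how a null primary result is read.

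**What to change.** 1. Replace the ESS sentence in the power paragraph with the figure for the primary contrast. Suggested text: *With 101 participants at 6 months the trial has 90% power for d = 0.65 (80% for d = 0.56); with 140, 90% power for d = 0.55 (two-sided alpha 0.05, no credit taken for baseline adjustment).* Confirm the alpha and state it. Keep 227 and 0.43 only if labelled as the treatment effect averaged over the three visits.
2. Add the randomisation stratum (comorbid non-tobacco SUD, Section D.3) to the Aim 1 and Aim 3 models, none of which lists it, and add baseline drinking to the abstinence models. This may recover some precision; the gain cannot be computed from the documents. In the logistic models the added covariates change the conditional odds ratio being estimated, so the choice should be written down before outcome data are analysed.

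The first change is wording only, at the price of a less favourable detectable effect. The second changes covariate lists. Neither needs more participants or visits, and the primary endpoint stays as it is.
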